9.4.2 Primary Performance Endpoint

Performance of HemoCareTM Hemodialysis System will be assessed by weekly stdKt/V_{urea} that will be collected every two weeks during each Evaluable Period. A successful weekly stdKt/V_{urea} is defined as a value of at least 2.0. If there is a retest of stdKt/V_{urea} for a

particular week (e.g., a missed or damaged sample) then the retested value will be used for analysis.

During each Evaluable Period, a binary outcome variable will be defined to be 1 if the weekly stdKt/Vurea for a given week meets the success criteria and 0 otherwise. For each subject, this will result in approximately 5 binary outcome values for each period. Each subject will be considered as meeting the primary performance endpoint for that period if all weekly stdKt/Vurea values meet the performance success criterion. A Non-inferiority test will be conducted. The difference in proportion of subjects (P1-P2) meeting the performance criteria in the Unassisted Evaluation Period (P2) and the Assisted Evaluation Period (P1) will be reported with a two-sided 90% CI.

$$H_0: p_1 - p_2 \ge \delta$$

 $H_1: p_1 - p_2 < \delta$

If the upper bound of the Confident interval is less than δ =0.10 then the null Hypothesis is rejected and non-inferiority is demonstrated.

The analysis will be carried out on the PP population. In addition, an analysis using the ITT population and the impact of missing data on the PP analysis will be explored as sensitivity analyses.

Multiple imputation (MI) will be used to assess the sensitivity of missing data on the ITT population. A MI logistic regression model for the efficacy success of each treatment-week will include the following factors: treatment, age, site, and weeks on home dialysis.

A risk difference analysis with continuity correction for independent samples will be performed. Although this will be paired rates, the independent sample analysis will be conducted because it is highly expected not having any failure, at least on the assisted treatment evaluable period.

The same analysis will be conducted using the PP population.

Furthermore, the impact of missing data on the primary analysis, will be explored as sensitivity analysis for both, ITT and PP population.

The evaluation of the primary performance endpoint will be based on the results from the PP population and the ITT population.

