The Unassisted Home Evaluable Period will be a minimum of 34 HD treatments (5-10 hours per treatment) with treatments prescribed to occur every other day, as prescribed by the Investigator. If the subject must go longer than one day between treatments, the reason will be documented in the source documents. Subjects will conduct the Unassisted Home Evaluable Period treatments during their sleeping hours either at daytime or nighttime based on subjects' schedules. The care partner must be present during all treatments during this period. Subjects will record how long they slept during dialysis in the Treatment Flowsheet.

Investigators will ensure the subjects' prescriptions achieve dialysis adequacy targets per local standard of care and that any prescription modifications will be done according to an established prescription change policy and will be recorded in the care plan.

During this period subjects and/or care partners will be exclusively responsible for administering treatments. The Medical Professional will be available via telephone for support, but will not administer treatments during this period. The Medical Professional will speak with the subject and/or care partner at least once per week during this period to determine and document the

occurrence of any AEs. During the Weekly Assessment, the subject and/or care partner will be prompted to report any adverse events that may have been experienced to ensure current and active capturing of the AEs. In addition to the AE data, clinical data will be collected during this phase including medication use, pre- and post-dialysis weights, blood pressures, respiratory rate, body temperature, and heart rate. Biochemical data (including complete blood count, iron profile, comprehensive metabolic panel, serum phosphorus, serum albumin, and serum urea) will be collected at least monthly during this period. Additionally, weekly stdKt/V_{urea} will be assessed every two weeks during this period.

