7.2.6 Kt/V

Weekly stdKt/Vurea will be calculated from pre- and post-dialysis urea levels during each evaluable period. Blood samples will be obtained every two weeks during each Evaluable Period. A central laboratory will be used for the analysis of the blood samples. If the weekly stdKt/Vurea goal is not met, the reason will be recorded.

Study personnel will be trained to obtain the pre- and post-treatment blood samples based on the Kidney Disease Outcome Quality Initiative Guidelines for sample collection.

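### The stdKt/V retest rule in section 9.4.2 is not limited to unusable samples, so as worded a valid value below 2.0 could be replaced in the primary performance analysis

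*Combined protocol and SAP*

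**What the plan says.** Section 9.4.2 (Primary Performance Endpoint) defines a successful weekly stdKt/V, which "is defined as a value of at least 2.0". Sampling is every two weeks, and for each subject "this will result in approximately 5 binary outcome values for each period". A subject succeeds in a period "if all weekly stdKt/Vurea values meet the performance success criterion". The difference in success proportions, Assisted minus Unassisted, "will be reported with a two-sided 90% CI". If the upper bound is below 0.10, "then the null Hypothesis is rejected and non-inferiority is demonstrated". The interval is a risk difference for independent samples with a continuity correction, chosen because failures are thought very unlikely, at least in the Assisted period.

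On retests, the same section says that for a "particular week (e.g., a missed or damaged sample) then the retested value will be used for analysis".

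Two other places bear on what follows a low value. Section 7.2.6 (Kt/V): "If the weekly stdKt/Vurea goal is not met, the reason will be recorded". Section 3.3, for both Evaluable Periods: "Investigators will ensure the subjects' prescriptions achieve dialysis adequacy targets per local standard of care".

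**The concern.** The retest sentence gives missed and damaged samples as illustrations, not as conditions. Read literally, any repeat for a given week displaces the earlier value, including a valid one below 2.0. The plan does not say when a repeat is allowed, how many are allowed, within what window, or which value counts when both are valid.

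The rule is neutral in wording but may not be neutral in use. The study is open-label and investigators are responsible for adequacy, so a low result is a likelier prompt for a repeat than a passing one. Because every value in a period must pass, replacing a subject's single low value turns a failure into a success. The sensitivity analyses in sections 9.4.2 and 9.7 address missing data only, so none would show what the original values gave.

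**Working it through.** **Inputs.** From section 9.4.2: threshold 2.0, about 5 values per period, all must pass, margin 0.10, two-sided 90% CI, independent samples with continuity correction. From section 9.2: 30 subjects per period, and power quoted at 98% and 99% subject success. Not in the documents, and therefore assumed: the share r of low values that are retested, and the chance q that a repeat after a low value is also low.

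**The plan's own figures.** The plan gives no figure for retests. Its only calculation for this endpoint is power: 91% at 99% success and 83% at 98%. Enumerating two independent binomial counts of 30 with no true difference gives 96.4% and 88.2% without the continuity correction, and 74.8% and 58.6% with it, so the stated figures were not reproduced. That is a separate matter. Only the 98% and 99% planning rates are used here.

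**Step 1: effect on subject failure at the planned rates.** With subject success S and 5 independent values, the failure chance per value is f = 1 − S^(1/5).
- S = 0.98: f = 0.00403.
- S = 0.99: f = 0.00201.

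If a share r of low values is retested, the failure chance per value becomes f × [1 − r(1 − q)], and subject failure is 1 − (1 − that)^5. With r = 0.5:

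| Repeat after a low value | S = 0.98 | S = 0.99 |
|---|---|---|
| No retests | 2.0% | 1.0% |
| Independent (q = f) | 1.0% | 0.5% |
| Low again half the time (q = 0.5) | 1.5% | 0.75% |
| Low again 80% of the time (q = 0.8) | 1.8% | 0.9% |

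In 30 subjects, the largest of these changes is 30 × (0.020 − 0.010) = 0.3 of a subject.

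**Step 2: leverage of one subject on the decision.** Upper limit = (p1 − p2) + 1.645 × √[p1(1 − p1)/30 + p2(1 − p2)/30] + 1/30, where the last term is the continuity correction.
- 30/30 against 29/30: 0.0333 + 1.645 × 0.0328 + 0.0333 = 0.121. Above 0.10, fails.
- 30/30 against 30/30: 0 + 0 + 0.0333 = 0.033. Below 0.10, passes.

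Without the correction the switch comes one subject later: 30/30 against 28/30 gives 0.142 and fails, while 30/30 against 29/30 gives 0.087 and passes.

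**Step 3: how often that leverage is in play.** With 30/30 in the Assisted period, the corrected interval passes only if the Unassisted period is also 30/30. At 98% Unassisted success and independent subjects, the chance of at least one failing subject is 1 − 0.98^30 = 45.5%. At 99% it is 1 − 0.99^30 = 26.0%.

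**Step 4: direction.** Replacing a low value raises the success proportion of its own period. If the Assisted period has almost no failures, there is almost nothing to erase there. Equal use of the rule in both periods would then act mainly on Unassisted failures and lower P1 − P2.

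**The case against.** The strongest reply is that the text points to unusable samples. Both examples are cases with no usable original result. Section 7.2.6 says what happens when the goal is missed, namely that a reason is recorded, and it orders no repeat. Section 3.3 concerns prescriptions, and for the Unassisted period it refers to an established policy for changing them. A sample drawn after a prescription change is doubtful as a retest for the same week. All of this stands, and it limits the point to what the wording permits. It does not close the gap, because the operative sentence still applies to any retest.

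A reader might infer large effects. A 2% failure chance per value would give subject failure of 1 − 0.98^5 = 9.6%, falling to 0.2% if every low value is retested. That implies 90.4% subject success, below the 95% to 99.5% range that the plan simulated, and it treats every low value as independent noise. A reader might also take the case at the margin, with true success 100% against 90%. There the chance of a false non-inferiority claim is 0.90^30 = 4.2%, rising to 9.6%, 21.5% or 46.8% if repeats convert 25%, 50% or 75% of failing subjects. The arithmetic is right, but the documents support neither those conversion shares nor that true state.

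Nor do they support a claim that home sampling is the source of asymmetry. The Assisted period is also preferably at home, and sections 7.2.6 and 8.3.2 provide for a central laboratory, trained collection and qualified in-home collectors.

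Finally, section 9.1 defers analysis conventions to a SAP and section 8.3.2 defers sample handling to a laboratory manual. No separate text on retests was available for this review. If one already limits them, the limit only needs to be carried into section 9.4.2.

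**Conclusion.** The point holds as a defect in a stated analysis rule. Section 9.4.2 lets a repeat displace a valid value below 2.0, nothing supplied prevents it, and no planned analysis would reveal it. The documents do not show that such repeats are intended or expected, and a reader should not infer that they are.

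The average effect is small at the planning rates: at most a halving of 2.0% or 1.0% subject failure when half of low values are retested, and less if low values recur. It matters because the decision is so sensitive. With 30 subjects per period and the continuity correction, one erased failing subject moves the upper limit from 12.1% to 3.3%, across the 10% margin. Since hardly any Assisted failures are expected, the likely direction favours non-inferiority.

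These figures assume 30 analysed subjects per period, five values each, independence between subjects and values except where q is varied, and an illustrative retest share of one half.

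**What to change.** Replace the retest sentence in section 9.4.2 with a rule of this content: a retest value enters the analysis only when no valid original result exists for that week. That means the sample was missed or lost, or was documented as damaged or invalid by the central laboratory or the collector, on grounds independent of the stdKt/V result and recorded before it. Where a valid original result exists, it is analysed and the retest is only listed.

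The timing condition is needed. Without it, a low sample could still be declared damaged after its result is known.

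The change affects only which value is analysed. It does not restrict repeat testing or any clinical response to a low result. The cost is one sentence in the protocol and SAP and a recorded validity status for samples declared damaged or invalid. The downside is that the observed success rate may be slightly lower.

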9.2 Determination of Sample Size

The goal is to have at least 1000 HemoCare™ treatments in both Evaluable Periods, in agreement with the FDA, to make a *clinical determination* of the safety of HemoCare™ based on the rate and type (i.e., device related) of AEs documented. To achieve this goal, at least 30 subjects will enter the Assisted Evaluable Period. No more than 25% of the total study subjects who complete the study may be enrolled at one site. Assuming each Evaluable Period is 3.5 treatments per week (one treatment every other night), each patient is expected to contribute 34 treatments to each Evaluable Period and 68 evaluable treatments to the study.

Based upon the number of treatments and the expected rate of adverse events, the current study design is under-powered to detect a clinically meaningful (less than 10%) non-inferiority margin for the Unassisted Evaluable Period.

For the primary performance endpoint, 'success' is defined as a subject who has all stdKt/Vurea measures in an evaluable period greater than or equal to 2.0. Several sets of simulation samples were generated (2,000 samples per set) assuming a rate of success between 95% and 99.5% for the Assisted Evaluable Period treatments paired with some fewer successes for the Unassisted Evaluable Period treatments. The success rate of the 2 periods were compared and the CI interval for the differences were calculated. With 30 subjects in each Evaluable Period, a margin of 10% will provide 91% power to declare non-inferiority if the actual success rate is 99% and 83% power if the actual success rate is 98%.

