9.3 Analysis Populations

The Per Protocol (PP) population will include all subjects and subject data that meets the following criteria specified below:

- 1. Each subject must not have any enrollment violations defined as failure to meet one or more inclusion criteria or meeting one or more exclusion criteria.
- Each subject must receive at least 34 treatments with HemoCare™ in each evaluable study period. All treatments that are initiated with HemoCare™ will be counted regardless of the length of the dialysis session.
- 3. For subjects who meet criteria 1 and 2 above, all adverse events that occur in each Evaluable Period will be counted.

The PP population will be used for analyses of the primary safety endpoint and primary performance endpoint.

The Intent-to-Treat (ITT) population will include all subjects who have used the HemoCare™ at least once during the Assisted Evaluable Period.

Poolability of the data will be examined by assessing the heterogeneity of the primary endpoint results across sites with 5 or more subjects enrolled.

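### The performance non-inferiority limit, on its usual reading, collapses to 1/n when nobody fails: it holds 5% at the planned 30 subjects but not at all other per-protocol sizes

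*Combined protocol and SAP*

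**What the plan says.** Section 9.4.2 scores a subject, separately by period, as a success or a failure: "Each subject will be considered as meeting the primary performance endpoint for that period if all weekly stdKt/Vurea values meet the performance success criterion", the criterion being a value of at least 2.0. P1 is the Assisted proportion and P2 the Unassisted. A two-sided 90% CI is reported for P1-P2, and "If the upper bound of the Confident interval is less than δ =0.10 then the null Hypothesis is rejected and non-inferiority is demonstrated". This is a nominal one-sided 5% test.

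On method, the section says "A risk difference analysis with continuity correction for independent samples will be performed". It admits that the data are paired and justifies the choice because "it is highly expected not having any failure, at least on the assisted treatment evaluable period". It names neither the interval nor the form of the correction.

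The analysis is run on the per-protocol (PP) population. Section 9.3 requires PP subjects to have no enrollment violations and at least 34 treatments "in each evaluable study period. All treatments that are initiated with HemoCare™ will be counted regardless of the length of the dialysis session". On numbers, Section 9.2 says "To achieve this goal, at least 30 subjects will enter the Assisted Evaluable Period", and the synopsis allows up to 70 enrolled so that about 30 enter the Unassisted Period. Section 5.3 makes replacement of discontinued subjects conditional on the enrollment or treatment targets being missed. Section 9.4.2 sets no minimum PP size and gives no check of the false-positive rate.

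**The concern.** A Wald-type limit estimates its standard error from the observed failures, so it is least reliable when there are none, and that is the outcome the plan expects. The upper limit is then only the continuity correction. It passes the 0.10 margin for any n of 11 or more (1/11 = 0.091), whatever the data can exclude. The reported interval would look much more precise than it is. If PP attrition takes the analysed number below 29, non-inferiority on a primary endpoint could be declared from data that do not exclude a true 10-point loss at the 5% level.

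**Working it through.** **Inputs.** Margin 0.10, two-sided 90% CI (z = 1.645), continuity-corrected risk difference for independent samples (9.4.2); 30 subjects per period (9.2). Assumed, because the plan is silent: unpooled Wald standard error, correction (1/n1 + 1/n2)/2 = 1/n, equal n in both periods.

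**Rule.** With f1 Assisted and f2 Unassisted failures among n subjects, declare non-inferiority if

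(f2 - f1)/n + 1.645 × sqrt[(f1/n)(1 - f1/n)/n + (f2/n)(1 - f2/n)/n] + 1/n < 0.10.

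**The plan's own figure.** For 30 subjects per period Section 9.2 gives the power as follows: "a margin of 10% will provide 91% power to declare non-inferiority if the actual success rate is 99% and 83% power if the actual" (the second case being 98%). Summing binomial probabilities over all (f1, f2) that pass, at equal true rates and n=30, gives 74.8% and 58.6% with the correction, and 96.4% and 88.2% without it. Neither pair reproduces 91% and 83%.

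**Zero failures.** With f1 = f2 = 0 the square root is zero and the limit is 1/n: 0.033 at n=30. The exact one-sided 95% upper limit for 0 failures in 30 is 1 - 0.05^(1/30) = 0.095. Zero failures exclude a 10% failure rate at one-sided 5% only if 0.9^n ≤ 0.05: 0.9^28 = 0.0523, 0.9^29 = 0.0471, so n ≥ 29.

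**One Unassisted failure, no Assisted failure.** The limit is 1/n + 1.645 × sqrt[(1/n)(1 - 1/n)/n] + 1/n: 0.1206 at n=30 (fails), 0.1006 at n=36 (fails), 0.0979 at n=37 (passes). Exact 5% control with one failure needs P(X ≤ 1 | n, 0.10) ≤ 0.05, which is first met at n=46 (0.0480).

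**False-positive rate** at a true 10-point loss, by enumeration, in percent:

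| True Assisted vs Unassisted success | n=20 | n=25 | n=30 | n=37 |
|---|---|---|---|---|
| 100% vs 90% | 12.2 | 7.2 | 4.2 | 10.4 |
| 99.5% vs 89.5% | 10.9 | 6.3 | 3.7 | 8.8 |
| 99% vs 89% | 9.7 | 5.5 | 3.4 | 7.6 |
| 98% vs 88% | 7.8 | 4.3 | 3.3 | 5.8 |
| 95% vs 85% | 4.2 | 2.8 | 3.3 | 3.7 |

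The first row can be checked by hand. Only zero failures pass at n = 20, 25 and 30, so the rate is 0.9^n: 0.1216, 0.0718, 0.0424. At n=37 it is 0.9^37 + 37 × 0.1 × 0.9^36 = 0.1036. At n=28 it is 5.2% and at n=36 2.3%. Independence between periods does not matter in the first row, because the Assisted Period then has no failures. A paired model in which every Assisted failure also fails Unassisted gives similar or lower values in the other rows.

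**The case against.** **The plan never says Wald.** True. A continuity-corrected Newcombe interval also fits the words. With no failures at n=30 its limit is 0.111, so it fails, and at 100% versus 90% its false-positive rate is 0% at n = 20, 25 and 30. But it would have only about 19% power at n=30 and 99% success, which cannot be squared with the stated 91%, and it would fail on the very result the plan expects. Wald is the better reading, though still an inference.

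**The rule is sound at the planned size.** This stands. A reader might infer that the primary test is invalid as designed; at n=30 its maximum rate is 4.2%, and a no-failure result passes under an exact test too.

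**Small PP sets are guarded against.** In part. Reading the target of 1000 treatments as applying to each period (30 × 34 = 1020), 20 subjects supply only 20 × 34 = 680, so replacement would probably be triggered and n near 20 is unlikely. But 28 completers supply 28 × 34 = 952, and partial completers, who are outside PP, can make up the other 48. Sizes just below 29 remain quite possible. Equally, 70 enrolled is meant to yield about 30, so 37 analysed is possible but not targeted.

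**The rates are worst case.** They are: 100% Assisted success lies outside the 95% to 99.5% range used in planning, although it matches the expectation of no Assisted failures and is where the maximum falls for the sizes of 20, 25, 30 and 37 tabulated.

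**ITT is also evaluated.** Section 9.4.2 bases the evaluation on both populations but also calls ITT a sensitivity analysis, and states no joint decision rule. The ITT analysis would use the same limit.

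**Does the rule reward attrition?** A reader might infer so, since at 99% success in both periods the chance of passing is 81.8% at n=20 against 74.8% at n=30. It is 94.0% at n=40, so a fall from 40 to 30 lowers it. The documents do not support a general claim.

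**Conclusion.** The concern holds in a limited form. On the usual reading, the interval reported for the expected no-failure result is far too narrow (0.033 against about 0.095 at n=30), and control of the 5% level depends on how many subjects are analysed. It holds at the planned 30. In the worst case it is missed trivially at 28 (5.2%), modestly at 25 (7.2%) and clearly at 20 (12.2%). The 10.4% at n=37 is a separate effect: one Unassisted failure starts to pass there, nine subjects before exact control allows it.

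These figures rest on the Wald reading with a 1/n correction and on true Assisted success at or near 100%; at 95% versus 85% none of the tabulated rates exceeds 5%. It would go too far to treat 12% as the trial's expected error rate, or to blame the Wald form for everything: at n=25 an uncorrected Newcombe or score limit also passes zero failures (0.0977) and gives the same 7.2%. What is missing is a limit valid at few failures, or a minimum n. This should be corrected, but it does not undermine the planned design.

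**What to change.** In Section 9.4.2 and the synopsis, keep the 0.10 margin and the one-sided 5% level, and name the limit from an exact unconditional non-inferiority test in place of the continuity-corrected risk-difference limit. An uncorrected score or Newcombe limit is not enough, because it leaves n=25 at 7.2%. State what the rule means when no Assisted failures occur: no Unassisted failures in at least 29 analysed subjects, or at most one in at least 46. Report the exact false-positive rate at the analysed n, state how the PP and ITT results combine into one decision, and recompute the power in Section 9.2 under the named limit.

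The cost is wording and programming, with no new patients or data. The decision at n=30 with no failures is unchanged. The real downside is that with fewer than 29 analysed subjects and no Assisted failures, non-inferiority could not be declared even with no Unassisted failure.

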With an underlying goal to have at least 1000 HemoCareTM Hemodialysis System treatments in both Evaluable Periods, at least 30 subjects will enter the Assisted Evaluable Period. No more than 25% of the total study subjects who complete the study may be enrolled at one site. Each patient is expected to contribute at least 68 evaluable treatments to the study (at least 34 in each Evaluable Period).

Based upon the number of treatments and the expected rate of adverse events, the current study design is under-powered to detect a clinically meaningful (less than 10%) non-inferiority margin for the Unassisted Evaluable Period.

For the primary performance endpoint, 'success' is defined as a subject who has all stdKt/Vurea measures in an evaluable period greater than or equal to 2.0. Several sets of simulation samples were generated (2,000 samples per set) assuming a rate of success between 95% and 99.5% and no actual difference between the two Evaluable Treatment Periods. The success rate of the 2 periods were compared and the CI interval for the differences were calculated. With 30 subjects in each Evaluable Period, a margin of 10% will provide 91% power to declare non-inferiority if the actual success rate is 99% and 83% power if the actual success rate is 98%.

Analysis Populations:

The Intent-to-Treat (ITT) population set will include all subjects who have used HemoCareTM Hemodialysis System at least once during the Assisted Evaluable Period.

The Per Protocol (PP) population will include all subjects not having any enrollment violations and receiving at least 34 treatments in each Evaluable Period. The PP population will be used as sensitivity analyses of the primary safety endpoint and primary performance endpoint.

Poolability of the data will be examined by assessing the heterogeneity of the primary endpoint results across sites with 5 or more subjects enrolled.

Primary Safety Endpoint:

The AE rate per 100 HemoCare™ Hemodialysis System treatments of Unassisted Home Evaluable Period will be compared to that of the

Assisted Evaluable Period and a two-sided 90% CI will be generated for the rate ratio (λ_2/λ_1) comparing the relative difference in AEs for the two Evaluable Periods using a negative binomial regression model.

Primary Performance Endpoint:

Performance of the HemoCare™ Hemodialysis System will be assessed by weekly stdKt/Vurea that will be collected every two weeks during each Evaluable Period.

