9.4 Primary Endpoints

9.4.1 Primary Safety Endpoint

The primary safety analysis will be to compare the Unassisted Home Evaluable Period AE rate per 100 HemoCareTM Hemodialysis System treatments against the Assisted Evaluable Period AE rate per 100 HemoCareTM Hemodialysis System treatments. A two-sided 90%

CI will be generated for the rate ratio $(\lambda 2/\lambda 1)$ comparing the relative difference in AEs for the two scenarios using a negative binomial regression model. The analysis will be carried out on the ITT population. The response variable is the total number of AEs. The model will include an indicator variable that is equal to one if treatment is "Assisted Evaluable Period" and zero otherwise. In addition, the log of the number of treatments will be included as an offset variable in the model and a subject specific random effect for treatment period will be included with covariance structure specified as "unstructured."

Let $\lambda_i = \frac{n_{aei}}{N_{txi}}$ be the rate of adverse event during treatment $i = \{a \text{ for assisted treatment} \}$ $\{a \text{ for unassisted trreatment} \}$

Where:

 $n_{aei} = Number \ of \ adverse \ event \ during \ treatment \ i, and \ N_{txi} = Number \ of \ treatment \ type \ i$

Given a non-inferiority margin δ ,

$$H_0: \frac{\lambda_u}{\lambda_a} > 1 + \delta$$
 $H_1: \frac{\lambda_u}{\lambda_a} \le 1 + \delta$

The Negative Binomial distribution will be used as a link function with the log transformation will be used to estimate the ratio and it's Confidence Interval. The logarithm of the Number of treatment for each treatment modality will be included as an offset term to account for any potential unpredicted unbalance between the two modalities sample sizes. If the Negative Binomial model fail to converge, the Poisson distribution with Scale =Dispersion will be adjusted.

Let UCI be upper boundary of the $\frac{\lambda_u}{\lambda_a}$ ratio confidence interval. H_0 is rejected if UCI $\leq 1 + \delta$ resulting in accepting H_1 and concluding Unassisted treatment are not inferior than assisted treatment.

The same analysis will be conducted using the PP population.

The evaluation of the primary safety endpoint will be based on the results from the ITT population and the PP population.

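### The Summary and section 9.4.2 contradict each other on which population decides the primary performance test, and no stated rule covers disagreement between PP and ITT

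*Combined protocol and SAP*

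**What the plan says.** Five statements bear on the performance endpoint.

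- Protocol Summary, Analysis Populations: "The PP population will be used as sensitivity analyses of the primary safety endpoint and primary performance endpoint".
- Section 9.3: "The PP population will be used for analyses of the primary safety endpoint and primary performance endpoint". PP is neither ranked against ITT nor called a sensitivity set.
- Section 9.4.2, after the hypotheses: "The analysis will be carried out on the PP population", followed by "an analysis using the ITT population and the impact of missing data on the PP analysis will be explored as sensitivity analyses".
- Section 9.4.2, after the paragraph on the risk difference with continuity correction, which names no population: "The same analysis will be conducted using the PP population".
- Section 9.4.2, last sentence: "The evaluation of the primary performance endpoint will be based on the results from the PP population and the ITT population".

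Safety is handled in a clear order. In 9.4.1, "The analysis will be carried out on the ITT population"; the analysis is then repeated on PP, and the evaluation uses both sets.

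The sets are defined differently. ITT needs one use of the device in the Assisted Evaluable Period. PP needs no enrollment violation and at least 34 treatments in each Evaluable Period (9.3).

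**The concern.** The Summary makes PP supportive. The opening of 9.4.2 makes PP the test set and ITT supportive. The later repeat on PP makes sense only if the paragraph before it concerned some other set. The last sentence gives both sets a part in the conclusion. A reader cannot tell from this whether PP decides, or both sets must pass, or ITT takes precedence as the Summary hints.

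The sets can differ on the events that decide the test. Section 5.3 lists inadequate dialysis among the possible reasons for withdrawal. A subject withdrawn before the 34th Unassisted treatment leaves PP, and any stdKt/V below 2.0 already recorded goes too. ITT keeps that value. The trial is open-label and expects almost no failures, so a single subject's inclusion can change the answer. If the deciding set is left open, it can be chosen after the results are known.

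**Working it through.** **The statements compared**

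| Place | PP | ITT |
|---|---|---|
| Summary | sensitivity | not named as primary; implied at most |
| 9.3 | used for both primary endpoints, unranked | defined only |
| 9.4.2, opening | carries the test | sensitivity |
| 9.4.2, after the risk-difference paragraph | repeat of an analysis on an unnamed set | – |
| 9.4.2, last sentence | basis of evaluation | basis of evaluation |

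Row 1 contradicts row 3. Row 5 does not fit a sensitivity label on either set. This part needs no calculation.

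**Can the choice of set change the result?**

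Inputs from the plan: margin 0.10, two-sided 90% interval for P1−P2 (Assisted minus Unassisted success), independent-samples risk difference with continuity correction (9.4.2), and 30 subjects (9.2). Section 9.4.2 prints no formula, so I assume a Wald interval with a 1/n correction. With p1 and p2 the observed success proportions, q = 1−p, and n subjects in each period:

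upper bound = (p1−p2) + 1.645 × √(p1q1/n + p2q2/n) + 1/n.

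- Failure dropped from PP, 0/29 vs 0/29 failures: 0 + 0 + 1/29 = 0.0345. Met.
- Same failure counted in ITT, 0/30 vs 1/30: 0.0333 + 1.645 × √(0.0333 × 0.9667/30) + 0.0333 = 0.0333 + 0.0539 + 0.0333 = 0.1206. Not met.
- Without the 1/n term: one counted failure gives 0.0333 + 0.0539 = 0.0872 (met). Two give 0.0667 + 0.0749 = 0.1416 (not met).

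The sets can also split the other way. If one failing subject completes and stays in a PP set of 30, the bound is 0.1206 (not met). In an ITT set of 37 whose 7 extra subjects all score as successes, it is 0.0270 + 0.0439 + 0.0270 = 0.0979 (met). The 37 and the scoring are assumptions.

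**The plan's power figures**

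The plan quotes 91% power at 99% success and 83% at 98%, for 30 subjects and a 10% margin, without naming the population. Exact enumeration with equal true rates, as the Summary assumes, gives 96.4% and 88.2% uncorrected, and 74.8% and 58.6% corrected. The quoted figures are not reproduced from the stated inputs. That is a separate matter, and nothing here depends on it.

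**Chance of meeting the margin under each rule**

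Exact enumeration with 30 subjects, 1% failure in each period, failures independent between periods (assumed), and a share s of subjects who fail in either period withdrawn and so lost from PP. With all failures counted the chance is 74.8% corrected and 96.4% uncorrected.

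| s | PP alone, corrected | PP alone, uncorrected |
|---|---|---|
| 10% | 76.9% | 97.0% |
| 25% | 80.2% | 97.9% |
| 50% | 86.2% | 99.0% |

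Requiring both sets, corrected and with low values recorded, gives 74.7, 74.6 and 74.6% at these shares.

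**The case against.** The strongest reply is that the last sentence of 9.4.2 already settles the matter: it rests the evaluation on both sets, as 9.4.1 does for safety, and the natural meaning is that both must pass. A recorded ITT failure would then count even if PP lost it. Much of this stands, and the fix adopts that reading. But the sentence does not state a both-must-pass rule, and it sits badly with calling ITT (9.4.2) or PP (Summary) a sensitivity analysis.

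A second reply is that 9.1 defers further detail to a statistical analysis plan, and the text reviewed contains no separate plan that states a rule. One may exist there. It would not remove the contradiction between the Summary and 9.4.2.

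A reader might go further and infer any of three things that the documents do not support.

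- **A seriously inflated false-claim rate.** If PP alone decided, with 10% Unassisted and 0% Assisted failure, the corrected rate would be (0.9 + 0.1s)^30: 4.2, 5.9, 9.6 and 21.5% at s = 0, 10, 25 and 50%. The plan gives no s. If both sets must pass and low values are recorded, the rate is 4.2% at every s. Withdrawal for inadequate dialysis is only a listed possibility, and stdKt/V is measured every two weeks (6.1.4), so a low value would often be on record.
- **ITT alone is the Summary's primary set for performance.** The Summary never says so; it only calls PP a sensitivity set.
- **Imputation would turn failures into successes.** The model "will include the following factors: treatment, age, site, and weeks on home dialysis", with no term for withdrawal reason. But 9.4.2 uses multiple imputation to assess sensitivity to missing data, and 9.7 adds single imputation for both sets.

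**Conclusion.** The contradiction between the Summary and 9.4.2 is plain from the text, and confidence in it is high. The point is worth correcting because it concerns the set behind a primary decision.

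The size is less certain. Under the assumed corrected Wald interval, one subject's inclusion moves the bound from 0.034 to 0.121, across the margin of 0.10. Without the correction, two counted failures are needed. The rates by withdrawal share and the ITT set of 37 are illustrations, because the documents give neither the share nor the ITT size. They do not show that the trial would wrongly claim non-inferiority. They show that the answer can depend on a choice the text leaves open.

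**What to change.** Align the Summary, 9.3 and 9.4.2 on one rule, fixed before the data are seen and consistent with the last sentence of 9.4.2: non-inferiority on performance is claimed only if the upper bound is below 0.10 in both the PP and the ITT population. Name the population in the risk-difference paragraph, and remove the conflicting sensitivity labels for this endpoint. If a separate statistical analysis plan exists, it should state the same rule.

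This changes wording and needs no new data. The cost is a somewhat lower chance of meeting the margin than if PP alone decided: about 75% against 77 to 86%, at 99% success, 30 subjects, the corrected interval, and 10 to 50% of failing subjects leaving PP.

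Optional, and not needed to resolve the conflict: a sensitivity analysis that scores observed stdKt/V values below 2.0, and withdrawals recorded as due to inadequate dialysis, as failures. This concerns the analysis only. Building it into the main test would redefine the PP set and the endpoint, which is a separate decision.
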